7.6.6 Vital Signs

Summary statistics for vital sign measurements (seated systolic BP, seated diastolic BP, heart rate and body temperature) will be presented at study baseline, and prior and after infusion by scheduled visit and treatment group. At the end of the study report, summary statistics of vital signs measurements collected during OLE will be provided.

7.7 Other Analyses

7.7.1 Immunogenicity

Serum for anti-abatacept antibody titers are drawn at Days 1 and 113 during the double-blind period and at Day 56, 84 and 168 during the follow-up period. For this assay, for all summaries and listings unless specified otherwise, a positive relative to baseline immunogenicity response for ‘CTLA4 and possibly Ig’, ‘Ig and/or Junction Region’, respectively, is defined as:

- A missing baseline immunogenicity measurement and a positive laboratory reported immunogenicity response post-baseline.
- A negative laboratory reported baseline immunogenicity response and a positive laboratory reported immunogenicity response post-baseline.
- A positive laboratory reported baseline immunogenicity response and a positive laboratory reported immunogenicity response post-baseline that has a titer value strictly greater than the baseline titer value.

This definition will be applied for each antibody-reactivity separately.

All other ECL immunogenicity measurements will be classified as lack of positive (relative to baseline) immunogenicity response or negative immunogenicity response.

The number (and percentage) of subjects with positive samples relative to baseline will be provided. These summaries will be provided by antibody specificity, and overall. These summaries

will include frequencies by scheduled visit (including on-treatment, off-treatment and overall) and by treatment group and age group. The Day 1 measurement will be the baseline measurement for all subjects.

Immunogenicity during the follow up period will be analyzed as above and will be provided at the end of study report.

7.7.2 Pharmacokinetic Endpoints

Serum PK:

- Cmin (μ g/mL): Trough level serum concentration of abatacept on Days 1, 15, 29, 57, 85 and 113 will be tabulated by age group and study day. Geometric means and coefficients of variation will be presented.
- Cmax (μ g/mL): Maximum observed serum concentration on Day 85 in subjects receiving abatacept IV will be obtained and tabulated by age group. Geometric means and coefficients of variation will be presented.
- Tmax (h): Time to reach peak serum concentration of abatacept will be obtained and tabulated by age group. Medians and ranges will be presented by age group.
- AUC (TAU) (μ g·h/mL): Area under the serum concentration time curve over a dosing interval between Days 85 and 113 will be tabulated by age group. Geometric means and coefficients of variation will be presented.
- Urine PK: Xu (μ g): Amount of abatacept excreted in urine for Days 1, 15, 29, 57, 85 and 113 will be tabulated by age group. Geometric means and coefficients of variation will be presented.

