Laboratory Assessments										
CBC	X		X		X				X	
Chemistry panel	X	X	X	X	X				X	
eGFR	X								X	

Table 5.1-2: Double Blind Period

Visit Day	Day 1	Day 15	Day 29	Day 57	Day 85 ^a	Day 92 (PK Visit)	Day 99 (PK Visit)	Day 106 (PK Visit)	Day 113 or Early Termination	Notes
[REDACTED]	X			X					X	
Urine sample for protein/creatinine ratio	X	X	X	X	X				X	Taken from a 24-hour urine collection on Day 1 and 113; if not possible, then from a single voided specimen. Taken from a single voided specimen at all other time points. A single voided specimen is also required at Day 1 and Day 113. For single voids, morning collections are preferred.
Urinalysis	X								X	Testing performed locally.
Urine pregnancy test	X	X	X	X	X				X	Testing performed locally on WOCBP subjects only
[REDACTED]										
[REDACTED]	■	■			■				■	
[REDACTED]	■									[REDACTED]
[REDACTED]	■	■			■				■	
[REDACTED]	■	■			■				■	
[REDACTED]	■	■	■	■	■				■	
[REDACTED]	■	■	■	■	■				■	
[REDACTED]	■	■	■	■	■				■	

Table 5.1-2: Double Blind Period

Visit Day	Day 1	Day 15	Day 29	Day 57	Day 85 ^a	Day 92 (PK Visit)	Day 99 (PK Visit)	Day 106 (PK Visit)	Day 113 or Early Termination	Notes
Pharmacokinetics and Immunogenicity										
Pharmacokinetic Sampling in Blood	X*	X*	X*	X*	X*	X**	X**	X**	X	* The samples will be collected both prior to dosing and at the end of infusion. ** The samples will be collected during the PK visit. All the PK assessments are specified in Section 5.4.1 .
Pharmacokinetic Sampling in Urine	X	X	X	X	X				X	To be taken from a 24-hour urine collection on Day 1 and 113; if not possible, then from a single voided specimen. From a single voided specimen at all other time points. A single voided specimen is also required at Day 1 and Day 113. For single voids, morning collections are preferred. The samples will be collected prior to dosing.
Immunogenicity anti-Abatacept Ab testing	X								X	
Clinical Supplies										
Drug preparation by a pharmacist	X	X	X	X	X					
Abatacept/placebo dosing	X	X	X	X	X					

^a Pediatric subjects may early escape at Day 85 at the discretion of investigator (and consultation with the subject’s guardian) based on criteria specified in [Section 3.1.2](#). In such situations, the Day 85 will be the Early Termination visit.

^b If a subject does not consent to the use of their samples for additional research, their samples will be discarded after all protocol-specified testing has been completed (not to exceed 15 years).

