5.4 Pharmacokinetic Assessments

5.4.1 Pharmacokinetic: Blood and Urine Sample Collection

Table 5.4.1-1 lists the sampling schedule to be followed for the assessment of pharmacokinetics (blood and urine) as well as the immunogenicity.

The actual date and time of sample collection must be recorded. The volume of urine collection must be recorded. Every effort should be made to collect PK samples as close to the protocol-specified times as possible.

Table 5.4.1-1: Sampling Schedule					
Study Day	Time (Relative to Dosing) Hour	Time (Relative to Dosing) Hour: Min	PK Blood Sample	PK Urine Sample^a	Immunogenicity Sample
Double Blind					
1	0 (predose)	00:00	X	X	X
1	0.5 (postdose)	0.5:00	X		X
15	0 (predose)	00:00	X	X	
15	0.5 (postdose)	0.5:00	X		
29	0 (predose)	00:00	X	X	
29	0.5 (postdose)	0.5:00	X		
57	0 (predose)	00:00	X	X	
57	0.5 (postdose)	0.5:00	X		
85	0 (predose)	00:00	X	X	
85	0.5 (postdose)	0.5:00	X		
92	168	168:00	X		
99	336	336:00	X		
106	504	504:00	X		
113 (or Early Termination)	0 (predose)	00:00	X	X	X
Follow-Up Visits^b					
56 Days after Last Dose	1344	1344:00	X		X
84 Days after Last Dose	2016	2016:00	X		X
168 Days after Last Dose	4032	4032:00	X		X

^a To be taken from a 24-hour urine collection on Day 1 and Day 113. If not possible, the sample will be taken from a single voided specimen. Single voided specimens are to be taken at all other time points including Day 1 and Day 113. For single voids, morning collections are preferred.

^b Only for subjects discontinuing use of abatacept (off study and not on commercial abatacept).

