5.4.4 Pharmacokinetic Evaluation

The pharmacokinetics of abatacept will be derived from serum concentration versus time data. Individual subject pharmacokinetic parameter values will be derived by non-compartmental methods and summarized. Urinary abatacept determinations will be obtained primarily for the purpose of determining whether abatacept is excreted in urine in the setting of proteinuria and whether the amount of abatacept found in urine is related to the level of ongoing proteinuria. Volume of urine collection from single voids and the total volume of urine collection from 24-hr collections will be recorded so that amount of abatacept present in urine can be determined. The pharmacokinetic evaluations will be comprised of the following parameters:

Serum PK:

- C_{\min} ($\mu\text{g/mL}$): Trough level serum concentration of abatacept on Days 1, 15, 29, 57, 85, and 113)
- C_{\max} ($\mu\text{g/mL}$): Peak serum concentration of abatacept on Day 85
- T_{\max} (hr): Time to reach peak serum concentration of abatacept on Day 85
- **AUC (TAU)** ($\mu\text{g}\cdot\text{h/mL}$): Area under the serum concentration time curve in a dosing interval between Days 85 and 113 (TAU) = 28 days) where TAU = 28 days

Urine PK:

- X_u (μg): Amount of abatacept excreted in urine

[Redacted]

[Redacted]

[Redacted]

[Redacted]

[Redacted]

[Redacted text block]

[Redacted text block]

[Redacted text block]

[Redacted text block]

[Redacted text block]

[Redacted text block]

[Redacted text block]

[Redacted text block]

[REDACTED]

[REDACTED]

[REDACTED]

[REDACTED]

[REDACTED]

[REDACTED]

[REDACTED]	[REDACTED]
[REDACTED]	[REDACTED]
[REDACTED]	[REDACTED]
[REDACTED]	[REDACTED]
[REDACTED]	[REDACTED]
[REDACTED]	[REDACTED]

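### SAP 7.7.2 tabulates urinary abatacept in micrograms without separating single voids from 24-hour collections, and no visible analysis relates it to proteinuria

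*SAP*

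**What the plan says.** SAP 7.7.2 defines Xu as an amount in µg: "Amount of abatacept excreted in urine for Days 1, 15, 29, 57, 85 and 113 will be tabulated by age group". The statistics are stated next: "Geometric means and coefficients of variation will be presented". Age group and day are the only breakdowns. The section does not mention specimen type, collection duration, or scaling to creatinine. Protocol 8.4.5 adds only that Xu is summarised by collection time.

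The specimens are set out in Protocol 5.1 (Table 5.1-2):

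- Days 1 and 113: "To be taken from a 24-hour urine collection on Day 1 and 113; if not possible, then from a single voided specimen".
- Days 15, 29, 57 and 85: the sample comes "from a single voided specimen at all other time points".
- In addition: "A single voided specimen is also required at Day 1 and Day 113".

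Footnote a to Table 5.4.1-1 (Protocol 5.4.1) agrees: "Single voided specimens are to be taken at all other time points including Day 1 and Day 113". All urine PK samples are taken before dosing.

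Protocol 5.4.4 gives two purposes for the urine measurements. The first is "determining whether abatacept is excreted in urine in the setting of proteinuria". The second is to learn "whether the amount of abatacept found in urine is related to the level of ongoing proteinuria". The same section has urine volume recorded for both specimen types so that an amount can be calculated.

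**The concern.** The amount in one void and the amount in 24 hours are different quantities, even though both are in µg. SAP 7.7.2 gives them one label and one table. If the Day 113 row uses the 24-hour collection where it exists and a single void otherwise, two things follow. The series changes scale between Day 85 and Day 113, and the Day 113 cell mixes the two scales. A reader could take the step as rising urinary loss of drug when nothing has changed, or miss a real fall.

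The single-void rows are also hard to interpret by themselves. Volume is recorded and so is the time of sampling, but the visible text does not ask for the time since the previous void. A single-void amount therefore cannot be turned into an excretion rate.

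Finally, the second stated purpose concerns proteinuria, and the planned table is not set against any measure of it.

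**Working it through.** The documents state no figure for urinary abatacept, so there is nothing to reproduce. The check compares the texts and then works an illustration.

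**Inputs from the documents.** Specimen by day: Protocol 5.1 (Table 5.1-2) and 5.4.1 (Table 5.4.1-1, footnote a). Quantity and summary statistics: SAP 7.7.2. Purposes and recorded volume: Protocol 5.4.4.

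**Assumed inputs.** A single void holds h = 3, 4, 6 or 8 hours of urine. Excretion is constant over the day and between Days 85 and 113. A share f of subjects supplies a 24-hour collection on Day 113, and the rest supply a single void. The documents give neither h nor f.

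**Step 1: every subject's Day 113 value is from 24 hours (f = 1).** The Day 113 to Day 85 ratio caused by specimen type alone is 24/h.

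**Step 2: some use the fallback.** On the log scale the mean step is f × ln(24/h) + (1 − f) × ln(1), so the geometric-mean ratio is (24/h)^f. With f = 0.5 this is the square root of 24/h.

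**Step 3: a true 50% fall in excretion, with f = 1.** The ratio shown would be 0.5 × 24/h.

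| h (hours per void) | f = 1: 24/h | f = 0.5: (24/h)^0.5 | True 50% fall, f = 1: 0.5 × 24/h |
|---|---|---|---|
| 3 | 8.0 | 2.83 | 4.0 |
| 4 | 6.0 | 2.45 | 3.0 |
| 6 | 4.0 | 2.00 | 2.0 |
| 8 | 3.0 | 1.73 | 1.5 |

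In the last column a real halving appears as a rise in every row.

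**Step 4: the Day 113 single void is used.** Here f = 0, the ratio is (24/h)^0 = 1.0, and specimen type adds no step, provided voids hold similar hours of urine on both days.

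**Step 5: which case applies?** SAP 7.7.2 does not say. The protocol names the 24-hour collection first for Day 113, and SAP 8.1.1 gives it the same priority for proteinuria, so a programmer could well follow that order. SAP 8.5 averages laboratory samples repeated by accident on the same date. That rule is not meant for two planned specimens of different kinds, and averaging µg per void with µg per 24 hours would have no meaning.

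**Step 6: Day 1.** The sample is pre-dose, and prior abatacept is excluded (Protocol 3.3.2, item 2k). The expected amount is zero, and a geometric mean is undefined when values are zero. SAP 7.7.2 gives no rule for values below quantification.

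**Step 7: the two purposes.** Detectable amounts in either specimen type speak to the first. The second needs urinary abatacept set against proteinuria. SAP 7.7.2 and the visible part of Protocol 8.4.5 contain no such analysis.

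**The case against.** A reader might infer that the table is bound to show a jump at Day 113. The documents do not support that. A single void is required on Day 113 alongside the 24-hour collection, so a like-for-like series over Days 15 to 113 will exist, and the SAP does not rule out using it. The jump is possible, not certain.

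A reader might also infer that the urine data cannot serve their stated purpose. That is too broad. Whether abatacept reaches the urine at all can be read from detectable amounts. Only the relation to proteinuria is left unanswered, and the main reason is that the table is not set against UPCR. That would remain true with one specimen type throughout.

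Other points on that side also stand. Volume is recorded for both specimen types, so only the duration of a void is missing. The sizes rest wholly on assumed voiding; morning samples are preferred and may hold more hours of urine than an average void, which would reduce the ratio. The Day 1 matter is a table convention, and it applies equally to Day 1 Cmin in the same section. Parts of the protocol are redacted, so an analysis against proteinuria there cannot be excluded. The pharmacokinetic objective is only descriptive.

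These points limit the size and priority of the concern. They do not remove it: SAP 7.7.2 still permits two different quantities in one series, and the visible plan does not address the second purpose.

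**Conclusion.** The point holds as a gap in specification with a possible artefact. SAP 7.7.2 does not separate specimen types for an amount that depends on them. If the Day 113 24-hour value is used, specimen type alone inflates the step from Day 85 by about 3- to 8-fold with full 24-hour collection and by about 1.7- to 2.8-fold with half. If the Day 113 single void is used, the inflation is nil. These sizes assume constant excretion and 3 to 8 hours of urine per void, neither of which the documents give.

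Separately, a single-void amount is not an excretion rate, and the planned table cannot show whether urinary abatacept is related to proteinuria. The priority is low: this is one descriptive summary under a secondary objective.

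**What to change.** Amend SAP 7.7.2 as follows.

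- Tabulate single-void and 24-hour results separately.
- For single voids on Days 15, 29, 57, 85 and 113, report the abatacept-to-creatinine ratio and relate it descriptively to UPCR from the same visit.
- Report Xu in µg only for the Day 113 24-hour collections, and relate it to 24-hour protein or UPCR.
- For Day 1, report the number of subjects with detectable abatacept in place of a geometric mean.

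The cost is SAP wording, one derived variable and a little more analysis; the urine is already collected. Two cautions belong in the text. The abatacept-to-creatinine ratio and UPCR share a creatinine denominator, which can induce correlation by itself. Abatacept concentration against protein concentration in the same specimen is a useful check. It should also be confirmed that the PK and UPCR aliquots come from the same void: the collection rules match, but the documents do not state it.

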8 CONVENTIONS

8.1 Definitions

8.1.1 Renal Response

The renal response at a specific time point will be present if all the following criteria (composite renal index) are met at that time point:

PROTEINURIA: Reduction of baseline UPCR of $\geq 50\%$ and to less than 3.

RENAL FUNCTION: No worsening of baseline (Study Day 1) estimated glomerular filtration rate (eGFR) defined as within normal range if normal at baseline or $\geq 75\%$ baseline value if below normal at baseline.

eGFR determination will be based on the CKD-EPI⁶ for adults and the new Schwartz equation⁷ for children.

The CKD-EPI formula will be used to determine the eGFR for the adults and will be expressed as mL/min per 1.73m². The CKD-EPI formula is:

$$\text{eGFR} = 141 \times \min(\text{Scr}/k, 1)^\alpha \times \max(\text{Scr}/k, 1)^{-1.209} \times 0.993 \text{Age} \times (1.018 \text{ [if female]}) \\ \times (1.159 \text{ [if black]})$$

Where Scr is serum creatinine (mg/dL), *k* is 0.7 for females and 0.9 for males, α is -0.329 for females and -0.411 for males, min indicates the minimum of Scr/*k* or 1, and max indicates the maximum of Scr/*k* or 1, age in years.

The new Schwartz formula for use in children to determine eGFR, also expressed as mL/min per 1.73m², is:

$$\text{eGFR} = 39.1[\text{height(m)}/\text{Scr(mg/dl)}]^{0.516} \times [1.8/\text{cystatinC(mg/L)}]^{0.294} \times [30/\text{BUN(mg/dl)}]^{0.169} \times \\ [1.099]^{\text{gender}} \times [\text{height (m)}/1.4]^{0.188}$$

Gender = 1 if male and 0 if female

Normal eGFR is defined as eGFR equal or greater than the lower limit of normal (LLN) eGFR. For this study, the LLN eGFR for both adults and children is defined as 90mL/min per 1.73m².

Proteinuria assessment for primary and secondary endpoints will be obtained from 24 hour urine collections performed at baseline and Day 113. When a 24 hour collection is not possible, a single voided specimen (i.e., spot urine) will be utilized, preferably in the morning. For all other time points, the assessment will require a single void spot urine.

8.1.2 Complete remission

Complete remission at a specific time point will be present if all the following criteria are met at that time point:

PROTEINURIA: UPCR \leq 0.3.

RENAL FUNCTION: No worsening of baseline (Study Day 1) estimated glomerular filtration rate (eGFR) defined as within normal range if normal at baseline, or \geq 75% baseline value if below normal at baseline.

eGFR determination will be based on the CKD-EPI for adults and the new Schwartz equation for children as indicated in [Section 8.1.1](#) above.

8.1.3 Prednisone or Prednisone Equivalent Use

Systemic prednisone or prednisone equivalent medication (oral, intramuscular or intravenous) will consist of the following generic names of CS on the CRF page. Before unblinding a final review

of all medications will be performed to identify all prednisone equivalent medications and dose conversion if there is any.

- Prednisolone
- Prednisone
- Deflazacort
- Methylprednisolone
- Dexamethasone
- Hydrocortisone
- Betamethasone

The conversions of dosages of the prednisone equivalents are as follows:

- 1mg of prednisolone = 1mg of prednisone
- 1mg of deflazocort = 0.83mg of prednisone
- 1mg of methylprednisolone = 1.25mg of prednisone
- 1mg of dexamethasone = 6.67mg of prednisone
- 1mg of hydrocortisone = 0.25mg of prednisone
- 1mg of Betamethasone = 8.33mg of prednisone

For subjects who discontinued the double-blind period early, the last prednisone dose reported will be carried to Day 113.

Prednisone use at each scheduled infusion visit:

- Day 1: the total daily dose at Day 1.
- Day 15: average daily dose in mg from one day after Day 1 to the infusion date of Day 15.
- Day 29: average daily dose in mg from one day after infusion date of Day 15 to the infusion date of Day 29.
- Day 57 to Day 113: average daily dose in mg from one day after the date of prior infusion to the date of current infusion.
- If a scheduled infusion is missed, the target day will be used for the visit when calculating the average total daily dose at this visit.

8.2 Determination of Responders

For analyses of treatment differences in the proportions of subjects achieving a renal response or complete remission at specific time point, a conservative approach will be taken for subjects who prematurely discontinue prior to achieving the efficacy endpoint. That is, regardless of treatment group, these discontinued subjects will be considered as non-responders. Subjects with any missing renal response component will also be considered as non-responders.

8.3 Baseline Measurements

For all outcome measures, unless otherwise specified, the baseline value is the last assessment taken prior to the first infusion of double-blind treatment. In general, this is the assessment taken on or just before the administration of study medication (Day 1). For some variables that are also measured during screening such as vital signs and laboratory data, if Day 1 assessments are unavailable, then screening assessments will be used as baseline measurements. Adult BMI will be calculated from the screening height and the Day 1 weight while the pediatric BMI will be calculated from the Day 1 height and weight.

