6 STUDY PERIODS, TREATMENT REGIMENS AND POPULATIONS FOR ANALYSES

6.1 Study Periods

In this study, there are four study periods: screening period, double-blind period (DB), open label extension period (OLE), and follow-up period.

The following analysis periods defined below are for analysis purposes. The definitions below indicate the data to be included in the analysis of each specified period. Subjects discontinued during a specified period (DB or OLE) will be considered on-treatment for 56 and 42 days after the last dosing in that period for safety and efficacy analysis respectively. Follow-up period data will be included in one of the analysis periods depending on the time of completing the study.

Screening Period: Starts with the day of enrolment and ends prior or on the day of first dose of study medication (abatacept or placebo).

Double-Blind Period: Starts with the first dosing of double-blind study medication and ends 56/42 days (for safety/efficacy analysis) after the last dose of the double-blind period or the first dosing of OLE, whichever is earlier.

For subjects who completed Period 1 and entered Period 2 prior to Protocol Amendment 2, includes data from first dose date in Period 1 up to the first dose in Period 2.

Open Label Extension Period (OLE): Starts with the first dosing in the OLE and ends 56/42 (for safety/efficacy analysis) days after the last dose in the OLE.

Cumulative Abatacept Safety Period: Starts at the time of the first dose of abatacept (either in the double-blind period for the subjects randomized to abatacept or in the OLE for the subjects randomized to placebo) and continues up to 56 days post last dose of abatacept for safety (AE and laboratory summaries). The last abatacept dose can be last dose in double-blind period for subjects not treated in the OLE.

For subjects who completed Period 1 and entered Period 2 prior to the protocol revision:

- For subjects on abatacept during Period 1:
 - For subjects who do not enter OLE period: starts with the first dosing of Period 1 and ends 56 days after the last dosing of Period 1.
 - For subjects who enter OLE period: starts with the first dosing of Period 1 and ends 56 days after the last dosing of Period 1 combined with OLE period that starts with the first dosing in the OLE period and ends 56 days after the last dosing in the OLE period.
- For subjects on placebo during Period 1:

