7.5.3 Analysis of Secondary Efficacy Endpoints

- Mean change from baseline in UPCR at Day 113: Longitudinal (repeated measure) mixed model will be used to assess this endpoint. The model will include treatment group, UPCR baseline value and randomization stratification factors (genotype and age), time, baseline value by time interaction, time by treatment interaction as fixed effects and subject as a random effect. An unstructured covariance matrix will be used to model the correlation of the repeated measures within each subject. The SAS procedure PROC MIXED will be used with the restricted maximum likelihood (REML) method for estimation and the denominator degrees of freedom will be calculated according to the Kenward Roger method. Adjusted mean change

from baseline by treatment groups and associated standard errors (SE) will be presented as well as treatment differences versus placebo with 95% confidence intervals. A summary will be provided, presenting the mean change from baseline in UPCR at each time point in double-blind period as described above. In addition:

- Summary of mean change from baseline in UPCR at each time point during double-blind period and OLE will be provided. This summary will be descriptive without adjusting for stratification or baseline factors.
- Graphs of median percent change from baseline in UPCR during all periods will be presented.

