7.6.5 Laboratory Data

Safety summaries based on laboratory test results include evaluation of laboratory abnormalities and changes in laboratory test values from baseline (baseline definition is provided in [Section 8.3](#)).

Laboratory abnormalities will be summarized by treatment group for double-blind period and cumulative abatacept safety period as described in [Section 7.6](#).

Laboratory abnormalities are identified using a pre-defined set of marked abnormality (MA) criteria (listed in Safety Data Convention). The frequency of subjects with laboratory MAs during treatment based on pre-specified criteria will be tabulated by treatment group, for each analyte.

Laboratory measurements and their changes from baseline will be summarized by study day and treatment group, for protocol specified analytes. Subjects who have laboratory measures at baseline and corresponding measure on at least one scheduled visit following administration of study drug will be included in the laboratory analyte assessment. Note that not all subjects have laboratory determinations for all analytes at all visits, and therefore the sample size may vary from analyte to analyte at each time point.

In addition shift tables for the following laboratory tests will be provided. The categorical classifications of these tests will be determined based on the cut points specified below and cross-tabulation of classification between baseline and each of the scheduled visits will be presented by treatment group.

Selected laboratory safety summaries will be generated for the double-blind period and the cumulative abatacept safety period separately as described in [APPENDIX 2](#).

Table 7.6.5-1: Definitions of Analytes Cut Points

Analytes (Test Code)	Cut Point
Platelet Count (PLAT)	< 100 x 10 ⁹ c/L
	≥ 100 x 10 ⁹ c/L
Alanine Aminotransferase (ALT)	< 3 x ULN
	3 - ≤ 5 x ULN
	> 5 x ULN
Aspartate Aminotransferase (AST)	< 3 x ULN
	3 - ≤ 5 x ULN
	> 5 x ULN
Neutrophils (absolute)	< 0.5 x 10 ⁹ c/L
	0.5 x 10 ⁹ c/L - ≤ 15 x 10 ⁹ c/L
	≥ 15 x 10 ⁹ c/L
G-Glutamyl Transferase (GGT)	< 3 x ULN
	3 - ≤ 5 x ULN
	> 5 x ULN

Table 7.6.5-1: Definitions of Analytes Cut Points

Analytes (Test Code)	Cut Point
Serum albumin	≤ ULNA (normal)
	> ULNA (abnormal)
██████████	█ ██████████
	██████████
██████	█ ██████████
	██████████
eGFR	< 60mL/min/1.73m ²
	60 - 89mL/min/1.73m ²
	≥ 90mL/min/1.73m ²

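### For placebo-randomized subjects, abatacept-period laboratory shift tables and OLE changes in UPCR and albumin run from Day 1 and so include about 112 days on placebo (SAP 8.3)

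*SAP*

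**What the plan says.** SAP 8.3 applies its rule broadly, "For all outcome measures, unless otherwise specified", and the rule is that "the baseline value is the last assessment taken prior to the first infusion of double-blind treatment". In practice this is study Day 1, with screening as the fallback. SAP 7.6.5 covers "changes in laboratory test values from baseline (baseline definition is provided in" Section 8.3), and for the shift tables it states that "cross-tabulation of classification between baseline and each of the scheduled visits will be presented by treatment group". The visit-window tables in SAP 8.6 have one baseline row, Day 1, and count OLE visits from study Day 1.

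Elsewhere the SAP does restart the clock at abatacept. Under SAP 6.1 the cumulative abatacept safety period "Starts at the time of the first dose of abatacept", which falls "in the OLE for the subjects randomized to placebo", or in Period 2 for placebo subjects who switched before Amendment 2. The exposure formulas in SAP 7.4.1 follow the same logic.

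Table 9-2 marks laboratory shift tables for the double-blind, cumulative abatacept and OLE periods. It marks mean laboratory change for the double-blind period only. On efficacy, SAP 7.5.3 says: "Summary of mean change from baseline in UPCR at each time point during double-blind period and OLE will be provided". It adds a descriptive OLE albumin summary by treatment arm, and SAP section 9 carries UPCR and albumin changes into the end-of-study report.

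**The concern.** The analysis period and the exposure clock move to first abatacept for placebo-randomized subjects, but the baseline does not. A table for the abatacept period then compares a value on abatacept with one taken before placebo began.

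Consider a hypothetical placebo subject with eGFR 92 on Day 1, 70 on Day 113 and 70 at the end of the OLE. Nothing changed on abatacept, yet the shift table records a move from the 90-or-above class to the 60–89 class within the abatacept period. In the other direction, a fall in UPCR that happened on placebo stays in every later OLE change from baseline.

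At stake is what these tables can say about starting abatacept. In the current design, placebo-randomized subjects are the only ones whose first abatacept dose is in the OLE.

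**Working it through.** **The plan's own figure.** The one stated design figure is 90 subjects for 40% versus 12%, two-sided 5%, about 80% power (SAP section 5). With mean proportion 0.26, the uncorrected size per arm is [1.96 × √(2 × 0.26 × 0.74) + 0.842 × √(0.40 × 0.60 + 0.12 × 0.88)]² / 0.28² = 37.3, so 38. The continuity correction raises this to 45 per arm, or 90 in total, which matches. The point here uses only the 45 per arm and the 12%.

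**Placebo share of the interval.** Protocol 3.1.3 makes OLE Day 1 the same day as double-blind Day 113, so 113 − 1 = 112 days pass before first abatacept. At a visit on study day d, the share is 112 / (d − 1). Target days are from SAP Table 8.6-1.

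| Study day | Interval (days) | Placebo share |
|---|---|---|
| 141 | 140 | 80% |
| 169 | 168 | 67% |
| 197 | 196 | 57% |
| 225 | 224 | 50% |
| 253 | 252 | 44% |
| 281 | 280 | 40% |

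For placebo subjects who entered Period 2 before Amendment 2, the share is also 80% at Day 141 and falls to 112/392 = 29% at Day 393. For a pediatric early escape at Day 85 it is 84/112 = 75% after 28 days of open-label treatment and 84/252 = 33% after 168 days. With a pre-abatacept baseline it is zero at every visit.

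**Which displays are reached.**
- Shift tables, cumulative abatacept and OLE periods: reached. Among the readable analytes eGFR is the useful disease measure. The albumin cut point sits at the upper limit of normal, so low albumin is classed as normal and the table is uninformative on it. Protocol Table 5.1-3 schedules OLE eGFR only at OLE Day 169 or Early Termination. OLE Day 169 is study Day 281 (113 + 168), where the share is 40%.
- UPCR and albumin: reached in the OLE summaries, but not listed for the cumulative period.
- Mean laboratory change: not reached, since it is planned for the double-blind period only.
- Marked abnormalities: the criteria are in an external convention and cannot be checked.

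**Illustration on UPCR.** At the plan's 12% rate, 0.12 × 45 = 5.4, so about 5 placebo subjects would meet renal response at Day 113 before any abatacept. Response needs a fall of at least 50% and a value below 3 (SAP 8.1.1). From a baseline of 3 (the entry minimum) the fall is at least 1.5. From 7 it must exceed 4. No mean baseline UPCR is given. If all five started somewhere from 3 to 7 (assumption), they would move the mean of 45 by at least 5/45 × 1.5 = 0.17 to 5/45 × 4 = 0.44 units. The other 40 or so could offset or reverse this.

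**The case against.** A reader might infer that placebo-period decline will be reported as abatacept toxicity, or placebo-period improvement as OLE efficacy, with a predictable bias. The documents do not support that. The plan calls these changes from baseline and makes no claim that they arose on abatacept. OLE albumin is shown by treatment arm and shift tables by treatment group, and As-Treated grouping follows randomization with one exception. Former placebo subjects should therefore sit in their own column and leave the abatacept-randomized column untouched. Only the OLE UPCR summary leaves its grouping unstated. That summary also runs through both periods, so the Day 113 mean is visible beside the OLE means. The sign and size of any net effect cannot be derived.

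Day 1 also has a sound use. The OLE is meant to describe durability and stability of response, and response is defined against study Day 1. Replacing Day 1 everywhere would hide a sustained improvement and would put the arms on different baselines.

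A reader might extend the point to immunogenicity, where SAP 7.7.1 says "The Day 1 measurement will be the baseline measurement for all subjects". For placebo subjects Day 1 and Day 113 both precede abatacept, and no harm from using Day 1 is shown.

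Finally, SAP 8.3 is a default that names no period, parts of the SAP are redacted, and the affected displays are descriptive.

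All of this narrows the point without removing it. Separate columns do not take placebo time out of the former-placebo column. Cross-tabulating baseline against each visit also never shows movement from Day 113 to an OLE visit, so for eGFR the two phases cannot be separated from the planned tables.

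**Conclusion.** The point holds for a limited set of displays: the cumulative abatacept and OLE shift tables, chiefly eGFR, and the descriptive OLE changes in UPCR and albumin, in placebo-randomized subjects only. About 112 placebo days lie inside each such change, from 80% of the interval at Day 141 to 40% at Day 281 in the current design. Forty-five subjects is a ceiling that assumes every placebo subject is treated in the OLE or Period 2. The double-blind analyses, AE counts and power are unaffected. The conclusion rests on the readable text, in which no first-abatacept baseline is specified. It is a cheap improvement to what the abatacept-period tables can show, and does not threaten the trial's main result.

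**What to change.** In SAP 8.3 and 7.6.5, state that for placebo-randomized subjects the baseline for the cumulative abatacept and OLE laboratory shift tables is the last value before the first abatacept infusion. That is Day 113 or Early Termination, or the last value before the first Period 2 dose for subjects who switched before Amendment 2.

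In SAP 7.5.3 and section 9, keep the Day 1 display of OLE UPCR and albumin. Add a second display of change from the last pre-abatacept value for placebo-randomized subjects, and state that the OLE UPCR summary is by randomized arm, as albumin already is.

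Keep Day 1 for all double-blind analyses, for durability of response and for immunogenicity.

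The cost is one derived baseline flag and one additional descriptive table. Protocol Table 5.1-2 already collects UPCR, eGFR, chemistry and CBC at Day 113 or Early Termination, so no new data are needed. The drawback is that the two arms have different baselines in the shift tables, which a footnote should state.
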